6.3. Treatment Assignment

All enrolled subjects will be randomized initially to Cohorts 1, 2, 3 and 4 such that upon reaching 12 subjects total for all 4 cohorts, each cohort will contain 3 subjects. The experience of these 12 subjects has guided the further conduct of the study. Adverse events, safety labs and the rate of infusion reactions in individual cohorts will dictate the continuance of a specific cohort. After the completion of at least one treatment cycle the subject experience will be evaluated before enrollment is opened to all cohorts. The future enrollment will be randomized between all open cohorts.

At this time Cohorts 1-10 are closed to enrollment. Randomization into the remaining open cohorts will continue until the cohorts are closed due to enrollment reaching 6-20 subjects per cohort or due to the stopping rules for individual cohorts. Cohorts that have closed due to enrollment levels may be re-opened to increase the enrollment to the maximum total number of subjects permitted.

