19.5. New York Heart Association Functional Classification

- Class I: Patients have cardiac disease but without the resulting limitations of physical activity. Ordinary physical activity does not cause undue fatigue, palpitation, dyspnoea or anginal pain
- Class II: Patients have cardiac disease resulting in slight limitation of physical activity. They are comfortable at rest. Ordinary physical activity results in fatigue, palpitation, dyspnoea or anginal pain
- Class III: Patients have cardiac disease resulting in marked limitation of physical activity. They are comfortable at rest. Less than ordinary physical activity causes fatigue, palpitation, dyspnoea or anginal pain
- Class IV: Patients have cardiac disease resulting in inability to carry on any physical activity without discomfort. Symptoms of cardiac insufficiency or of the angina syndrome may be present even at rest. If any physical activity is undertaken, discomfort is increased

Study: SEL-212/201 Version: 7.1	Effective Date March 19, 2018
------------------------------------	----------------------------------

Revision History

Version	Reason for Change	Date
01	Original protocol	28JUL2016
02	Revised SEL-110 highest dose from 0.1 mg/kg to 0.08 mg/kg Updated Schedule of Events, Figure 1, Tables 7-9 Updated description of potential risks of SEL-110	05SEP2016
03	Revised methylprednisolone premedication dose from 16mg to 40mg, its route of administration from oral to intravenous and its timing from 2 hours to 1 hour prior to study drug administration Updated Individual and cohort stopping rules	07DEC2016
04	Revised fexofenadine premedication dose to 180 mg Revised gout flare premedication to colchicine 0.6mg QD Revised windows for screening and vital signs Updated Schedules of Events, Table 7 and dosing instructions Updated previous human clinical experience Updated Figure 1 for closure of Cohorts 1 and 2 Updated cohort randomization and opening criteria Added observational visit and T-cell recall assay	22DEC2016
05	Added Cohort 7 and 8 Adding optional alternative premedication for methylprednisolone Added weight measurement at all Day 21 visits Clarified T-cell recall sample collection schedule and requirements for sampling Revised inflammatory marker schedule Updated Schedules of Events and Table 8 Updated Figure 1 for inclusion of Cohorts 7 and 8 Clarified windows for dosing and infusion reaction kit samples	07FEB2017

Study: SEL-212/201 Version: 7.1	Effective Date March 19, 2018

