Mean time response profiles for uric acid concentration raw values and %CFB at each time point for each Treatment period and cohort plotted against time for each Cohort separately with curves for all Treatment periods overlaid on one plot. BLQ values for uric acid concentration will be assigned 0 values for linear scales and 1/10 of LLOQ values for all time points for the graphic representation on log-linear scales only. Actual measured concentrations will be presented on both linear and log-linear scales while %CFB profiles will be presented on linear scale only.

Box plots for each derived PD parameter based on actual measurements and %CFB: CFB_{min}, AUE_{CFBlast}, TA_AUE_{CFBlast} will also be plotted by treatment.

Individual profiles for uric acid concentration absolute values and %CFB will be plotted for each Treatment period and cohort on a separate plot.

9.7. ASSESSMENT OF THE EFFECTS OF SEL-110 (RAPAMYCIN) AND SEL-037 (PEGSITICASE) ON PD PARAMETERS OF URIC ACID

Assessments done outside the assessment windows may be excluded from summarization. This will be determined prior to database lock.

The key PD parameters based on measured values and %CFB %CFB_{min}, AUE_{%CFBlast}, and TA_AUE_{%CFBlast} as well as uric acid concentration and %CFB on day 21 of each treatment period will be analyzed using linear mixed model for the response to SEL-110 dose levels co-administered with either 0.2 or 0.4 mg/kg of SEL-037 (the dose level of SEL-110 for Cohorts 1 and 2 will be assigned as 0). Additionally contribution of SEL-110 to the PD effect of SEL-037 will be tested to compare the following (test - reference). For PD

Statistical Analysis Plan

parameters based on actual measured values baseline concentration of uric acid will be incorporated in the model as covariate.

For Parts A and B following contrasts will be tested:

Cohort 3 Part A vs Cohort 1 Part A
Cohort 5 Part A vs Cohort 1 Part A
Cohort 7 Part A vs Cohort 1 Part A
Cohort 4 Part A vs Cohort 2 Part A
Cohort 6 Part A vs Cohort 2 Part A
Cohort 8 Part A vs Cohort 2 Part A
Cohort 10 Part A vs Cohort 2 Part A
Cohort 12 Part A vs Cohort 2 Part A
Cohort 1 Part A vs Cohort 2 Part A
Cohort 3 Part A vs Part B
Cohort 5 Part A vs Part B
Cohort 7 Part A vs Part B
Cohort 4 Part A vs Part B
Cohort 6 Part A vs Part B
Cohort 8 Part A vs Part B
Cohort 10 Part A vs Part B
Cohort 12 Part A vs Part B

For Part C (cohorts 13, 15, 17) additional contrasts will be:

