$$Lower = 100 \times e^{(LowerBound (1-2*\alpha)\%CIs for theDifference)}$$

$$Upper = 100 \times e^{(UpperBound (1-2*\alpha)\%CIs for theDifference)}$$

GMR ratio outside equivalence criteria 80-125% will demonstrate (1) dose effect SEL-110; (2) synergy or additive effect of SEL-110 administration on PD by SEL-037. P-values will be generated for all contrasts. Values of $p < 0.05$ will indicate statistical significance of the effect.

The results of the comparisons will be graphically illustrated using box plots for Part A/B and comparison between Part C and B separately.

Correlations between PD endpoints (C_{min} , CFB_{min} , $AUE_{CFBlast}$, and $TA_AUE_{CFBlast}$) and PK parameters (C_{max} , AUC_{0-last} and AUC_{0-inf}) for both SEL-110 and SEL-037 will be explored using Spearman correlation analysis. The correlations for Part C treatment periods will be presented in the separate table.

The correlation between each of these PK (C_{max} , AUC_{0-last} and AUC_{0-inf}) and PD (C_{min} , CFB_{min} , $AUE_{CFBlast}$, and $TA_AUE_{CFBlast}$) parameters will also be explored and presented in a scatter plot with a regression line on it using simple linear regression which will have PK parameter as dependent variable and PD parameter as independent variable. The additional plots will be created for the Part C.

Example SAS code will be:

```
PROC GLM DATA=PKPDDATA;  
MODEL PD_parameter = PK_parameter;  
RUN;
```

Statistical Analysis Plan

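### Four uric acid contrasts in SAP 9.7 (7 v 1, 8 v 2, 10 v 2, 12 v 2) appear to have no concurrently randomised control, yet the SAP lets them establish a SEL-110 effect

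*SAP*

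**What the plan says.** The secondary objective covers SEL-037 given with and without SEL-110 (Protocol 5.2, SAP 3.2). Only Cohorts 1 and 2 receive SEL-037 without SEL-110.

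SAP 9.7 lists eight Part A contrasts of a SEL-212 cohort against SEL-037 alone: 3, 5 and 7 v 1, and 4, 6, 8, 10 and 12 v 2. Among them are "Cohort 7 Part A vs Cohort 1 Part A", "Cohort 8 Part A vs Cohort 2 Part A" and "Cohort 12 Part A vs Cohort 2 Part A". All eight are treated alike. The example code has treatment as its only fixed effect. The text adds baseline uric acid as a covariate, for measured-value parameters only. The reading rule is "GMR ratio outside equivalence criteria 80-125% will demonstrate (1) dose effect SEL-110", or else synergy or an additive effect, and p < 0.05 marks the effect as significant. SAP 8.7 fits a SEL-110 dose slope to SEL-037 PK, separately for the 0.2 and 0.4 mg/kg SEL-037 cohorts, with Cohorts 1 and 2 entered as dose 0.

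On allocation, subjects were first randomised to Cohorts 1-4, and after that "The future enrollment will be randomized between all open cohorts" (Protocol 6.3). The revision history gives the sequence:

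- Version 03, 07DEC2016: "Revised methylprednisolone premedication dose from 16mg to 40mg, its route of administration from oral to intravenous".
- Version 04, 22DEC2016: "Updated Figure 1 for closure of Cohorts 1 and 2". The same version revised the fexofenadine dose and the gout-flare prophylaxis.
- Version 05, 07FEB2017: "Added Cohort 7 and 8".
- Version 06.0, 12JUN2017: Cohorts 10 and 12 added. They were removed in 06.1 (28JUN2017) and added again in 06.2 (09AUG2017).

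**The concern.** Randomisation protects a comparison only between arms that were open together. If Cohorts 1 and 2 stopped enrolling before Cohorts 7, 8, 10 and 12 existed, these four contrasts compare different enrolment periods as well as different treatments. Sites, case mix and premedication may differ between the periods. Anything that shifts uric acid between them enters the contrast in full and cannot be told apart from SEL-110.

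The higher SEL-110 doses also entered later, so a stage difference would tilt the dose relation in the same way. The Phase 1 results in Protocol 4.3.2.3 link loss of uric acid control to anti-uricase antibodies, so a change in steroid exposure is a conceivable route for such a shift. What is at stake is the statement the SAP would make on the SEL-110 contribution, which is part of a secondary objective.

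**Working it through.** The documents state no power or error rate for these contrasts, so there is no planned figure to reproduce. The revision history is used here only to date design changes during enrolment.

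**1. Intervals between recorded versions**
- Steroid change to recorded closure of Cohorts 1-2: 07DEC2016 to 22DEC2016 = 15 days.
- Closure to Cohorts 7 and 8: 22DEC2016 to 07FEB2017 = 9 + 31 + 7 = 47 days.
- Closure to first addition of Cohorts 10 and 12 (12JUN2017) = 9 + 31 + 28 + 31 + 30 + 31 + 12 = 172 days.
- Closure to their re-addition (09AUG2017) = 9 + 31 + 28 + 31 + 30 + 31 + 30 + 31 + 9 = 230 days.

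**2. Classification of the eight contrasts**
- 3 v 1 and 4 v 2: these cohorts were randomised together from the start.
- 5 v 1 and 6 v 2: Protocol 6.3 opens further cohorts only after the first 12 subjects have been evaluated following at least one cycle, so any overlap is partial and its extent is not given.
- 7 v 1, 8 v 2, 10 v 2 and 12 v 2: the test cohort was created after the recorded closure. That is 4 of 8.

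**3. Effect of an unmodelled shift**

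Suppose SEL-110 has no effect and the control cohort differs by d SD because of its enrolment stage. A two-sided 5% two-sample t test then has non-centrality d / sqrt(1/n1 + 1/n2) on n1 + n2 - 2 degrees of freedom. For example, with 6 v 20 and d = 1.0, the non-centrality is 1 / sqrt(1/6 + 1/20) = 2.15 against a critical value of 2.06. False-positive rates:

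| n (control v test) | d = 0 | 0.25 | 0.5 | 1.0 |
|---|---|---|---|---|
| 6 v 6 | 0.050 | 0.068 | 0.123 | 0.347 |
| 6 v 20 | 0.050 | 0.081 | 0.178 | 0.541 |

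The sizes come from the planned 6-20 per cohort. The values of d are assumptions; the documents give no figure for a calendar or premedication effect.

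**4. Precision of the concurrent contrasts**

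By the same formula, power for a true 1 SD effect is 35% at 6 v 6. At 3 v 3, the allocation described for the first 12 subjects, it is 16%.

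**5. Precision cost of a stage term in a dose slope**

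Assume sizes 6, 8, 12, 12, 10 and 12 for Cohorts 2, 4, 6, 8, 10 and 12, with all of Cohort 2, half of Cohort 4 and one sixth of Cohort 6 in the earlier stage. The standard error of the change over 0-0.15 mg/kg, in SD units, rises from 0.44 without a stage term to 0.62 with one: 0.62 / 0.44 = 1.4 times.

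**The case against.** Several points on the other side are sound.

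- **Re-opening.** The Synopsis and Protocol 6.2 allow Cohorts 1-10 to be re-opened. Nothing says that Cohorts 1 and 2 were, and version 7.1 still marks them closed. But it cannot be said outright that no subject was ever randomised between them and the later cohorts.
- **Which steroid Cohorts 1 and 2 received.** A reader might infer that they started on 16 mg oral and had at most 15 days on the newer regimen. The documents do not establish this. First enrolment in October 2016 is an estimate. The 28 November 2016 statement in Protocol 10.1.1 concerns subjects given SEL-212 and pools two studies. Protocol 14.2 requires IRB approval before an amendment takes effect, so version dates are not site dates. Later doses in these cohorts may also have used 40 mg IV. Enrolment at least partly under earlier regimens is probable, no more.
- **Mechanism.** Protocol 8.2.1 gives the steroid's purpose as reducing infusion reactions. No section reports an effect on antibodies or uric acid.
- **Models.** It would be wrong to say that all cohorts lie on one dose line. SAP 8.7 fits the two SEL-037 doses separately, and the SAP 9.7 code uses treatment as a class factor.
- **Remedy.** A reader might expect a before/after-version-03 term to restore the 5% level. It does so only if the bias is exactly that step. It would not absorb drift through 2017 or the version 04 changes, and it may not be estimable.
- **Setting.** This is an open-label phase 2 trial with a safety primary objective. That supports a modest remedy, but it also argues against wording that treats these contrasts as proof.

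None of this supplies a concurrent control for the four contrasts or removes the reading rule.

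**Conclusion.** The point holds in limited form. On the recorded sequence, and unless Cohorts 1 and 2 were re-opened, 7 v 1, 8 v 2, 10 v 2 and 12 v 2 are comparisons with non-concurrent controls. The SAP neither says so nor adjusts, and its rule would credit any stage or premedication difference to SEL-110.

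The size and direction of the bias are unknown. The 12-54% range describes an assumed shift of 0.5 to 1.0 SD with 6 controls against 6 to 20 subjects; it does not estimate this trial's error rate. A reader might go further and infer that an observed SEL-110 effect would be an artefact. The documents do not support that: they give no evidence that a shift occurred. This should be changed in the SAP; it does not undermine the primary safety objective.

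**What to change.** 1. In SAP 9.7, label 7 v 1, 8 v 2, 10 v 2 and 12 v 2 as non-concurrent, non-randomised comparisons. Take them out of the rule that reads a ratio outside 80-125% as a SEL-110 effect, and report them as descriptive estimates with confidence intervals.
2. Identify 3 v 1 and 4 v 2, among subjects randomised while Cohorts 1 and 2 were open, as the concurrently randomised contrasts. Include 5 v 1 and 6 v 2 only as far as enrolment dates overlap. State that precision is low and that 3 v 1 and 4 v 2 cover only 0.05 mg/kg SEL-110.
3. For the SAP 9.7 models and the SAP 8.7 slopes, add a sensitivity analysis with enrolment stage or premedication regimen at first dose (protocol version), where estimable.
4. Tabulate enrolment dates and premedication regimen by cohort. If Cohorts 1 and 2 were re-opened, this table will show the overlap.

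**Cost.** No new data are needed, only SAP wording and recorded dates. Intervals in the sensitivity analysis widen, by about 1.4 times for the slope in the assumed layout above. The SEL-110 statement becomes weaker at 0.1 mg/kg and above, where these contrasts are the only comparison with SEL-037 alone in the list. The stage term may not be estimable and would not remove all calendar drift; in that case the labels and the table carry the caution.

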SEL-212 (0.08 + 0.4 mg/kg) Cohort 6 Part A	SEL-037 (0.4 mg/kg) Cohort 6 Part B																																					
SEL-212 (0.1 + 0.2 mg/kg) Cohort 7 Part A	SEL-037 (0.2 mg/kg) Cohort 7 Part B																																					
SEL-212 (0.1 + 0.4 mg/kg) Cohort 8 Part A	SEL-037 (0.4 mg/kg) Cohort 8 Part B																																					
SEL-212 (0.125 + 0.4 mg/kg) Cohort 10 Part A	SEL-037 (0.4 mg/kg) Cohort 10 Part B																																					
SEL-212 (0.15 + 0.2 mg/kg) Cohort 11 Part A	SEL-037 (0.2 mg/kg) Cohort 11 Part B																																					
SEL-212 (0.15 + 0.4 mg/kg) Cohort 12 Part A	SEL-037 (0.4 mg/kg) Cohort 12 Part B																																					

Note: Cohort 9 is intentionally omitted from this protocol in order to maintain the cohort numbering convention of associating even numbered cohorts with the 0.4 mg/kg SEL-037 dose.

Overall scheme of trial (Part C)

SEL-212 (0.15 + 0.2 mg/kg) Cohort 13 Part C		
  
 Cohort	SEL-110	SEL-037	
   
13	0.15 mg/kg	0.2 mg/kg	
 
15 (first/induction dose)	0.15 mg/kg	0.2 mg/kg	
 
15 (4 subsequent doses)	0.1 mg/kg	0.2 mg/kg	
 
17	0.1 mg/kg	0.2 mg/kg	
  
	Cohort	SEL-110	SEL-037	13	0.15 mg/kg	0.2 mg/kg	15 (first/induction dose)	0.15 mg/kg	0.2 mg/kg	15 (4 subsequent doses)	0.1 mg/kg	0.2 mg/kg	17	0.1 mg/kg	0.2 mg/kg
Cohort	SEL-110		SEL-037														
13	0.15 mg/kg		0.2 mg/kg														
15 (first/induction dose)	0.15 mg/kg		0.2 mg/kg														
15 (4 subsequent doses)	0.1 mg/kg	0.2 mg/kg															
17	0.1 mg/kg	0.2 mg/kg															
SEL-212 (0.15 + 0.2 mg/kg) Cohort 15 Part C	SEL-212 (0.1 + 0.2 mg/kg) Cohort 15 Part C																
SEL-212 (0.1 + 0.2 mg/kg) Cohort 17 Part C																	

Note: Cohorts 14 and 16 are intentionally omitted from this protocol in order to maintain the cohort numbering convention of associating odd numbered cohorts with the 0.2 mg/kg SEL-037 dose.

Diagnosis and main criteria for inclusion/exclusion:

Inclusion Criteria:

1. Has provided written informed consent prior to the conduct of any study specific procedures and continues to provide consent;

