4.5.1. Rationale for Dose Selected (Part C)

Dosing in the Part C of this Phase II study (SEL-212/201) of up to 0.15 mg/kg SEL-110 in combination with 0.2 mg/kg SEL-037 (ie, SEL-212) is similarly supported by the nonclinical and clinical data presented in Section 4.3.1 and Section 4.3.2, respectively. From our review of interim serum uric acid and antibody data from Part A and B cohorts, we believe that 5 doses of the combination may be allow enhanced reduction of antibodies and serum uric acid for the duration of the therapy. Similar to Parts A & B, doses of 0.2 mg/kg SEL-037 were selected for Part C based on preclinical evaluation in rodent, rat, and monkey (Section 4.3.1.1) and clinical evaluation in two completed Phase I studies. Support for 3 doses of SEL-110 in combination with SEL-037 is described above for Part A and B. We have continued to extend our toxicology program to include additional doses of SEL-110 alone and in combination with SEL-037. We will submit toxicology data that demonstrates the safety of delivering 5 doses at up to 0.15 mg/kg SEL-110 prior to any patients receiving the 4th dose of SEL-212 in Part C. Should a delay occur such that the toxicology data to support the safety of the 4th and 5th doses of the combination of SEL-212 at the proposed doses is not available at the scheduled time of the 4th dose for a subject, that subject will be converted from the planned regimen of 5 doses of SEL-212 to a receive only SEL-037 at 0.2 mg/kg at the 4th and 5th dose and hence converted to a regimen of 3 doses of SEL-212 followed by 2 doses of SEL-037. This regimen is similar to the regimen of previous cohorts in Part A and B.

To investigate dose ranging in the 5 combination dosing regimen, Cohort 17 will have 5 doses of SEL-110 at a lower dose of 0.1 mg/kg at all 5 treatment periods and Cohort 15 will have 4 doses of SEL-110 at a lower dose of 0.1 mg/kg at treatment periods 2-5. Preliminary analyses of data in the Phase I study (SEL-212/101) and cohorts in Part A and Part B suggest that the first treatment period may be a critical time period for preventing antibody development to SEL-037; thus increased doses of SEL-110 in the first treatment period may help achieve a higher rate of patients who do not develop antibodies to SEL-037. As such, the first dose of SEL-110 in

treatment period 1 will be at a higher dose of 0.15 mg/kg in Cohort 15 to allow for comparison of efficacy and safety with other regimens in Part C.

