SEL-212 (0.05 + 0.4 mg/kg) Cohort 4 Part A	SEL-037 (0.4 mg/kg) Cohort 4 Part B																																					
SEL-212 (0.08 + 0.2 mg/kg) Cohort 5 Part A	SEL-037 (0.2 mg/kg) Cohort 5 Part B																																					
SEL-212 (0.08 + 0.4 mg/kg) Cohort 6 Part A	SEL-037 (0.4 mg/kg) Cohort 6 Part B																																					
SEL-212 (0.1 + 0.2 mg/kg) Cohort 7 Part A	SEL-037 (0.2 mg/kg) Cohort 7 Part B																																					
SEL-212 (0.1 + 0.4 mg/kg) Cohort 8 Part A	SEL-037 (0.4 mg/kg) Cohort 8 Part B																																					
SEL-212 (0.125 + 0.4 mg/kg) Cohort 10 Part A	SEL-037 (0.4 mg/kg) Cohort 10 Part B																																					
SEL-212 (0.15 + 0.2 mg/kg) Cohort 11 Part A	SEL-037 (0.2 mg/kg) Cohort 11 Part B																																					
SEL-212 (0.15 + 0.4 mg/kg) Cohort 12 Part A	SEL-037 (0.4 mg/kg) Cohort 12 Part B																																					

Note: Cohort 9 is intentionally omitted from this protocol in order to maintain the cohort numbering convention of associating even numbered cohorts with the 0.4 mg/kg SEL-037 dose.

Statistical Analysis Plan

Overall scheme of trial (Part C)

SEL-212 (0.15 + 0.2 mg/kg) Cohort 13 Part C	
SEL-212 (0.15 + 0.2 mg/kg) Cohort 15 Part C	SEL-212 (0.1 + 0.2 mg/kg) Cohort 15 Part C
SEL-212 (0.1 + 0.2 mg/kg) Cohort 17 Part C	

Cohort	SEL-110	SEL-037
13	0.15 mg/kg	0.2 mg/kg
15 (first induction dose)	0.15 mg/kg	0.2 mg/kg
15 (4 subsequent doses)	0.1 mg/kg	0.2 mg/kg
17	0.1 mg/kg	0.2 mg/kg

Note: Cohorts 14 and 16 are intentionally omitted from this protocol in order to maintain the cohort numbering convention of associating odd numbered cohorts with the 0.2 mg/kg SEL-037 dose.

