8.7. ASSESSMENT OF EFFECT OF VARIOUS DOSES OF SEL-110 ON PHARMACOKINETICS OF SEL-037

Effect of co-administration of various doses of SEL-110 on pharmacokinetics of SEL-037 PK parameters for serum concentrations or uricase activity for cohorts 1, 3, 5, 7, 11 (SEL-037 dose 0.2 mg/kg) and 2, 4, 6, 8, 10, 12 (SEL-037 dose 0.4 mg/kg) separately (SEL-110 dose in cohorts 1 and 2 will be set to 0) will be performed by a linear mixed-effect model:

$$PKparam(SEL - 037) = \alpha + s_i + \beta \times Dose(SEL - 110) + e_i$$

α : population mean intercept

β : population mean slope

s_i : random effect of subject i on the intercept, iid $N(0, \sigma_s^2)$

e_i : residual, iid $N(0, \sigma_e)$ for subject i

Statistical Analysis Plan

the PK parameters and dose of SEL-110 will not be log-transformed to allow inclusion of 0 dose of SEL-110 into the model

P value will be calculated for slope and intercept. If the p-value of the slope is less than 0.05, a direct relationship is declared. If p value for slope will be >0.05 the result will be interpreted as lack of effect of SEL-110 on pharmacokinetics of SEL-037.

SEL-110 co-administration effect will also be explored graphically with scatter plots of C_{max} , AUC_{0-last} and AUC_{0-inf} for SEL-037 serum concentrations or uricase activity vs dose levels of co-administered SEL-110 including 0 dose for placebo.

The example SAS code will be:

```
PROC MIXED DATA=data_set_name;  
CLASS treatment;  
MODEL PK Parameter = dose /DDFM=KR;  
LSMEANS dose / CL;  
RUN;
```

Additionally the effect of SEL-110 on PK of SEL-037 will be performed by comparison of data from Parts B vs Part C for treatment periods 4-5 using ANOVA model as described in the Section 8.6 of the SAP.

The contrasts will include:

- Cohort 13 treatment period 4 vs Cohort 11 treatment period 4
- Cohort 13 treatment period 5 vs Cohort 11 treatment period 5
- Cohort 15 treatment period 4 vs Cohort 11 treatment period 4
- Cohort 15 treatment period 5 vs Cohort 11 treatment period 5
- Cohort 15 treatment period 4 vs Cohort 13 treatment period 4
- Cohort 15 treatment period 5 vs Cohort 13 treatment period 5

Graphic presentation in the form of box plots will be also added to the exploratory analysis.

Statistical Analysis Plan

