Cohort 13 treatment period 4 vs Cohort 11 treatment period 4
Cohort 13 treatment period 5 vs Cohort 11 treatment period 5
Cohort 15 treatment period 4 vs Cohort 11 treatment period 4
Cohort 15 treatment period 5 vs Cohort 11 treatment period 5
Cohort 15 treatment period 4 vs Cohort 13 treatment period 4
Cohort 15 treatment period 5 vs Cohort 13 treatment period 5

Cohort 17 treatment period 4 vs Cohort 11 treatment period 4
Cohort 17 treatment period 5 vs Cohort 11 treatment period 5
Cohort 17 treatment period 4 vs Cohort 13 treatment period 4
Cohort 17 treatment period 5 vs Cohort 13 treatment period 5

Cohort 17 treatment period 4 vs Cohort 15 treatment period 4
Cohort 17 treatment period 5 vs Cohort 15 treatment period 5

Statistical Analysis Plan

Unstructured variance-covariance matrix will be used. If the model cannot converge or unable to make hessian positive definite, compound symmetry or other variance-covariance matrices will be explored and used.

Example SAS code will be:

```
PROC MIXED DATA=data_set_name;  
CLASS subject_id treatment;  
MODEL loge(PD Parameter) = treatment /DDFM=KR;  
RANDOM subject_id / TYPE=UN;  
LSMEANS treatment / DIFFS CL;  
RUN;
```

1. The following hypotheses will be tested:

- $H_{01}: \mu_T/\mu_R \leq 80\%$ vs. $H_{A1}: \mu_T/\mu_R > 80\%$
and
- $H_{02}: \mu_T/\mu_R \geq 125\%$ vs. $H_{A2}: \mu_T/\mu_R < 125\%$

If the 90% confidence interval (CI) for the geometric mean ratio (GMR) is within (80% - 125%) for any of the contrasts for C_{max} , AUC_{0-t} and AUC_{0-inf} , the null hypotheses, that is H_{01} and H_{02} , will be rejected and we will conclude that the Test (T) is equivalent to the Reference (R).

2. If bioequivalence cannot be established in step 1 above, the following hypothesis will be tested to explore noninferiority (1-sided test):

- $H_{01}: \mu_T/\mu_R \leq 80\%$ vs. $H_{A1}: \mu_T/\mu_R > 80\%$

If the lower 90% CI bound for the GMR is greater than 80% for C_{max} , AUC_{0-t} and AUC_{0-inf} , H_{01} will be rejected and we will conclude that the new therapy (T=Test) is no worse than the old therapy (R=Reference).

The formula for calculation of the estimated ratio between the test and reference and the $(1-2*\alpha)*100\%$ CI of the ratio is given below.

Difference = Estimate of difference between test and reference least square means

Statistical Analysis Plan

$$Ratio = 100 \times e^{Difference}$$

(1-2* α)*100% CIs for the Ratio:

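### SAP 9.7 reads Cohort 17 v 11 and 15 v 11 as tests of SEL-110's contribution, but both also differ in Period 1-3 SEL-110, and no listed contrast estimates continuation at 0.10 mg/kg

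*SAP*

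**What the plan says.** SAP 9.7 introduces its contrasts with a stated purpose: "Additionally contribution of SEL-110 to the PD effect of SEL-037 will be tested to compare the following (test - reference". Among the additional Part C contrasts it names "Cohort 17 treatment period 4 vs Cohort 11 treatment period 4", repeats it for Period 5, and lists Cohort 15 against Cohort 11 in the same two periods.

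The section also says how results will be read. A 90% confidence interval for the GMR inside 80-125% means equivalence. A GMR outside that range is taken to demonstrate a SEL-110 dose effect, or an additive or synergistic effect on what SEL-037 does. A p-value below 0.05 is significance. None of these rules is limited to particular contrasts.

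The regimens behind the contrasts are:

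- Cohort 11: "SEL-212 (0.15 + 0.2 mg/kg) Cohort 11 Part A", then "SEL-037 (0.2 mg/kg) Cohort 11 Part B" (SAP 3.7).
- Cohort 17: "Cohort 17 will have 5 doses of SEL-110 at a lower dose of 0.1 mg/kg at all 5 treatment periods" (Protocol 4.5.1).
- Cohort 7: "SEL-212 (0.1 + 0.2 mg/kg) Cohort 7 Part A" (Protocol synopsis), then "SEL-037 (0.2 mg/kg) Cohort 7 Part B" (SAP 3.7).

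In SAP 9.7, Cohort 7 appears only in a Part A comparison with Cohort 1 and in a comparison of its own Part A with its own Part B. It is never set against Cohort 17. SAP 8.7 states that "the effect of SEL-110 on PK of SEL-037 will be performed by comparison of data from Parts B vs Part C" in Periods 4-5. It lists 13 v 11, 15 v 11 and 15 v 13, and no Cohort 17 contrast.

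**The concern.** In Periods 4-5 the Part B cohorts have stopped SEL-110 and the Part C cohorts are still receiving it. A contrast between them shows what continued SEL-110 adds only if the two cohorts were treated alike up to Period 4. Cohort 13 v 11 meets that condition by plan. Cohorts 17 and 15 against Cohort 11 do not.

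The protocol itself gives reason to think the early dose matters. Section 4.5.1 describes the first treatment period as possibly critical for preventing antibodies to SEL-037. Section 4.5 links dose-dependent antibody inhibition to more sustained uric acid control. The early dose can also influence who meets the Day 21 uric acid criterion and is treated in Period 4 at all.

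Under the SAP's reading rule, a ratio near 1 could be reported as no contribution from SEL-110 when two effects have offset each other. A ratio away from 1 could be reported as a SEL-110 contribution in Periods 4-5 when it reflects the early dose.

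**Working it through.** **Planned SEL-110 by period (mg/kg; SEL-037 is 0.2 mg/kg throughout).** Sources: SAP 3.7 and Protocol 4.5.1.

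| Cohort | P1 | P2 | P3 | P4 | P5 | Sum P1-3 |
|---|---|---|---|---|---|---|
| 7 | 0.10 | 0.10 | 0.10 | 0 | 0 | 0.30 |
| 11 | 0.15 | 0.15 | 0.15 | 0 | 0 | 0.45 |
| 13 | 0.15 | 0.15 | 0.15 | 0.15 | 0.15 | 0.45 |
| 15 | 0.15 | 0.10 | 0.10 | 0.10 | 0.10 | 0.35 |
| 17 | 0.10 | 0.10 | 0.10 | 0.10 | 0.10 | 0.30 |

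Over Periods 1-3:

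- Cohort 17 v 11: 0.30/0.45 = 0.67, or 33% less.
- Cohort 15 v 11: 0.35/0.45 = 0.78, or 22% less.
- Cohort 17 v 7: 0.30/0.30 = 1.00.
- Cohort 13 v 11: 0.45/0.45 = 1.00.

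**What each contrast estimates.** Take a PD parameter scaled so that larger means more uric acid lowering, on the SAP's ratio scale. Let c10 and c15 be the ratios due to continuing SEL-110 at 0.10 or 0.15 mg/kg. Let e be the Period 4-5 ratio carried over from three early doses of 0.15 rather than 0.10. Then:

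- 13 v 11 = c15
- 17 v 11 = c10 / e
- 17 v 13 = c10 / (c15 × e), which is 17 v 11 divided by 13 v 11
- 17 v 7 = c10

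The three listed contrasts among Cohorts 11, 13 and 17 carry two independent pieces of information about three unknowns. Cohort 15 adds one more ratio, but also its own early-dose pattern and so another unknown. The listed contrasts therefore do not recover c10. Cohort 17 v 7 would.

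**Illustration, on assumed values.** The SAP states no effect size, SD or power for these contrasts, so there is no plan figure to reproduce. With c10 = 1.5, the expected 17 v 11 ratio is:

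- e = 1.0: 1.5/1.0 = 1.50
- e = 1.25: 1.5/1.25 = 1.20
- e = 1.5: 1.5/1.5 = 1.00
- e = 2.0: 1.5/2.0 = 0.75

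A two-sample t-test on the log scale was simulated 40,000 times per setting, as a simplification of the SAP's mixed model. It used 6, 13 or 20 subjects per cohort and log SD 0.2, 0.3 or 0.5. The middle column is 13 per cohort with SD 0.3.

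| Assumed truth | Result on 17 v 11 | n = 13, SD 0.3 | Range over n and SD |
|---|---|---|---|
| c10 = 1.5, e = 1 | p < 0.05 | 0.91 | 0.25 to 1.00 |
| c10 = 1.5, e = 1.5 | p < 0.05 | 0.05 | about 0.05 throughout |
| c10 = 1.5, e = 1.5 | equivalence declared | 0.18 | 0.00 to 0.93 |
| c10 = 1, e = 1.5 | p < 0.05, Cohort 17 lower | 0.91 | 0.25 to 1.00 |

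The first row is also what 17 v 7 would give at c10 = 1.5, whatever e is. The sizes 6 to 20 are the enrolled range for Part A/B cohorts. The numbers reaching Period 4 are not given and may be smaller.

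**The case against.** **Purpose.** Protocol 4.5.1 presents Cohort 17 as dose ranging within the five-dose combination and Cohort 15 as a comparison with other Part C regimens. 17 v 13, 17 v 15 and 15 v 13 serve those aims and are listed. 17 v 11 is a legitimate comparison of whole regimens. This stands, but the SAP places 17 v 11 under the contribution of SEL-110 and applies an attribution rule that a whole-regimen comparison cannot support.

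**Decomposition.** Since 17 v 11 is the product of 17 v 13 and 13 v 11, an offset could show as two opposing components. This stands in part: it helps interpretation but yields no continuation estimate at 0.10 mg/kg.

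**Code.** The example code requests all pairwise treatment differences, so 17 v 7 might be printed if Cohort 7 is in that dataset. An unnamed difference in the output is not a planned contrast.

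**Cohort 7 as reference.** A reader might infer that Cohort 7 had exactly Cohort 17's treatment under the same rules. The documents support a match on planned dose only.

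- The revision history adds Cohort 7 in February 2017, updates individual stopping rules in April 2017 and clarifies infusion rates at 0.10 mg/kg in June 2017, so some Cohort 7 subjects may have been treated under earlier text.
- SAP 3.8 gives a single steady rate at 0.10 mg/kg in Period 2, whereas Protocol 9.5 gives a two-step rate from 0.10 upwards.
- Cohort 7 closes after 5 stopped subjects, Cohorts 11 and 17 after 10 (Protocol 6.3.1).
- Cohort 11 is still enrolling under protocol version 7.1, so it is closer in time to Part C.

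This stands: 17 v 7 may be biased as well as imprecise. It does not make 17 v 11 answer the continuation question.

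**Cancellation.** A reader might also infer that 17 v 11 will hide a real effect. The documents give neither c10 nor e. Because Period 4 is open only to subjects who met the Day 21 criterion, selection could shrink or change e. Offset is a possibility, not a finding.

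**Conclusion.** The point holds as one of attribution and omission. Cohort 17 v 11 and 15 v 11 mix less early SEL-110 with more late SEL-110, so the SAP 9.7 rule that reads the ratio as a SEL-110 effect is not justified for them. A continuation estimate at 0.10 mg/kg is missing, although a cohort with the same planned doses through Period 3 exists.

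The dose differences (33% and 22% less over Periods 1-3) come directly from the documents. The effect on the estimate is unknown, and the ratios and probabilities under working are illustrations on assumed values. That the early dose carries over into Periods 4-5 is an expectation drawn from the protocol, not a stated result.

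Severity is modest. The primary objective is safety, and these are secondary PD contrasts with no powered hypothesis behind them.

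**What to change.** In SAP 9.7:

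- Add Cohort 17 treatment period 4 vs Cohort 7 treatment period 4, and the same for period 5.
- Name 13 v 11 and 17 v 7 as the SEL-110 continuation contrasts, at 0.15 and 0.10 mg/kg.
- Keep 17 v 11 and 15 v 11 as whole-regimen comparisons, and state that the rule attributing a GMR outside 80-125% to SEL-110 does not apply to them.
- State how Part C subjects converted to SEL-037 alone at doses 4 and 5 (Protocol 4.5.1) are handled. A converted Cohort 17 subject has Cohort 7's planned regimen and must not count as continued.
- State beside 17 v 7 that Cohort 7 is closed and non-concurrent, that few of its subjects may reach Period 4, and that some may have been treated under earlier stopping or infusion text.

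In SAP 8.7, label 15 v 11 as a whole-regimen comparison too. The infusion-rate passages at 0.10 mg/kg in SAP 3.8 and the protocol must be reconciled. A pooled continuation estimate stratified by SEL-110 dose is optional.

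The cost is SAP wording. Uric acid is already sampled in both cohorts in Periods 4-5. The drawback is that 17 v 7 will be imprecise and open to calendar-time bias, so it should be reported with its interval and not read alone.
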